8. STUDY PARAMETERS

The 16 participating Iowa SUD organizations will be assigned to the

- Control arm (typical Product Training/On-line Support alone, n=8 organizations, n=20 sites) or
- Treatment arm (NIATx-TI framework plus Product Training/On-line Support, n=8 organizations, n=20 sites)

We will use a stratified randomization (or blocking with matched pairs). The matching criteria, using organizational characteristics and technology adoption traits, are:

- a) Innovation score per organization
- b) # of rural sites (due to the digital divide in these areas)
- c) # of outpatient sites per organization.

The innovation score per organization will be calculated based on the level of "success" (i.e. volume of patient enrollment) the organization had with implementing an online gambling portal in 2014. The implementation of the online gambling portal was in partnership with the Iowa Department of Public Health, who will provide gambling project enrollment numbers. This is an objective and relevant measure for innovativeness of the organizations as we will be implementing a mobile technology that will require the organizations to disperse the technology to their patients.

We will apply urn randomization to achieve arm balance, using these 3 traits (e.g., # above/below mean for each trait or # of outpatient sites). An organization from each matched pair will be assigned to a study arm. Organizations (and their staff and patients) will have access to A-CHESS for the duration of the study regardless of which arm they are randomized to. Organizations and staff in the treatment arm will have access to NIATx-TI for 36 months.

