9. STATISTICAL CONSIDERATIONS

Sample Size, Power & Data Analysis Plan: We will fit a mixed-effects model with the appropriate link function (e.g., linear, log) to the monthly results for the performance measures, % of eligible A-CHESS users and frequency of A-CHESS use, for each of the participating organizational sites, clustered by organization, and estimate the NIATx-TI framework and

product training effects. A mixed-effect model offers 2 advantages over conventional regression models: 1) The mean outcomes for a given treatment organization are expected to be correlated from month to month. A mixed-effect model allows for auto-correlated error terms. 2) Many unobservable treatment organizational site characteristics are likely to influence the key measures. Random effects at the treatment organization site level can be employed within the mixed-effect model to capture the correlation introduced by such characteristics. Proper reflection of auto-correlation and random effects allows for more reliable estimates of the fixed effects, starting at baseline, then again during the 18-month test and post-test periods. The power of the study design is determined by the anticipated standardized effect size based on effects experienced in the IRHIT project. The standardized effect size is calculated following Cohen's definition of mean effect size divided by effect size standard error.⁶⁵ The higher the standardized effect size, the more powerful the study design. Historically, cluster-randomized trials portray the standardized effect sizes of 0.2, 0.5 and 0.8 as small, medium, and large respectively. The IRHIT pilot data found that NIATx-TI increased client technology use rates by 12.4% (increase of intervention success), which can be transformed into Cohen's $d = 0.352$.⁶⁶ Intraclass correlation (ICC) among sites affects the power of cluster-randomized trials.⁶⁷ An estimate of ICC is around 0.10.⁵⁰ With a total of 8 organizations, with 20 organizational sites in each arm, where each site has an average 62 eligible patients, the study will achieve a power of .90 with a type I error rate of 0.05.

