Mediational (and Maintenance) analysis: We will examine the mediating effects of organizational factors of: % of counselors using A-CHESS, organizational readiness (via OCM), financial resource availability (via Klein's inventory), and A-CHESS implementation readiness on A-CHESS use through a causal mediational analysis, using data from end of intervention periods. These factors will be analyzed using mixed-effects models. Through a mediation analysis,^{68,69} we can estimate the direct (A-CHESS use with NIATx TI and Product Training) and indirect effects (Adoption and Implementation factors) of each implementation arm on A-CHESS use. We will test the mediation effect of each potential mediator at each time point as well as across time. The R package 'mediation,' will estimate the causal mediation effects, examine moderated mediation effects, and conduct sensitivity analysis.⁷⁰

Effectiveness analysis: We will compare a retention rates in the 2 different arms using hierarchical linear models, where arm membership is used as the treatment assignment. We will examine the distribution of this outcome measure and will implement an appropriate transformation or nonlinear link function when appropriate (e.g., logistic, Poisson, exponential). Monthly data collection of the Effectiveness as well as Reach (A-CHESS Use) measures, allows for analysis after each stage of NIATx-TI.

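### With 16 organizations randomized, the Reach and retention models leave the form of the organization term and the small-sample reference unspecified, and the 0.90 power counts 40 sites as independent

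*Combined protocol and SAP*

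**What the plan says.** Section 8 makes the organization the unit of allocation: "An organization from each matched pair will be assigned to a study arm". There are 8 organizations and 20 sites in each arm. Section 5 places both members of a pair in the same staggered cohort.

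In section 9 the Reach model is a mixed-effects model of monthly results "for each of the participating organizational sites, clustered by organization", with auto-correlated errors. The one random effect it names is introduced as an advantage of this class of model: "Random effects at the treatment organization site level can be employed within the mixed-effect model". Retention, under Effectiveness analysis, is compared "using hierarchical linear models, where arm membership is used as the treatment assignment", with no levels listed. For neither model does the plan give a degrees-of-freedom method, a small-sample correction or a permutation test. It also does not say whether the pair or the three matching traits enter.

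The power statement takes the pilot effect, "which can be transformed into Cohen's $d = 0.352". It says "Intraclass correlation (ICC) among sites affects the power of cluster-randomized trials", sets the ICC at about 0.10, and gives no separate value for organizations. It continues "With a total of 8 organizations, with 20 organizational sites in each arm, where each site has an average 62 eligible patients" and concludes that "the study will achieve a power of .90 with a type I error rate of 0.05".

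**The concern.** The arm effect varies only between organizations, so its standard error should carry the between-organization variance, and its reference distribution should reflect 16 randomized units. Section 9 indicates the first without saying how, and is silent on the second. A random intercept, a robust variance or a plain description of the data layout would each fit the words used for Reach. The wording for retention is looser still. Analysts following the text in good faith could therefore report different p-values and intervals for the main comparison.

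The power statement reinforces a site-level reading, because its only ICC and its cluster count both sit at site level. It also gives a more favourable figure than an analysis by randomized unit would.

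**Working it through.** **Inputs from section 9:** d = 0.352 (so SD = 1), ICC 0.10, 62 patients per site, 20 sites and 8 organizations per arm, alpha 0.05. Sidedness is not stated; two-sided is used here. Average sites per organization: 20/8 = 2.5.

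**Step 1. Reproduce the stated power with the site as cluster.**
- Design effect = 1 + (62 − 1) × 0.10 = 7.10.
- Effective n per arm = 20 × 62 / 7.10 = 174.6.
- Noncentrality = 0.352 × √(174.6/2) = 3.289.
- Power = 0.908 (normal), or 0.893 on 40 − 2 = 38 df. This matches 0.90.

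Using the 43 patients per site given in section 3 instead of 62 gives 0.893 (normal), so that difference hardly matters here.

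**Step 2. Same ICC with the organization as cluster.** Cluster size is 2.5 × 62 = 155 and the design effect is 1 + 154 × 0.10 = 16.4. Effective n per arm is 8 × 155 / 16.4 = 75.6, and power is 0.581 (normal). This does not match 0.90.

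**Step 3. Three levels.** Let ρ be the correlation between patients at different sites of one organization. The documents do not give it, so it is assumed, with the within-site ICC held at 0.10. The design effect is 1 + 61 × 0.10 + (2.5 − 1) × 62 × ρ. The t reference has 16 − 2 = 14 df, with no credit for matching.

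| ρ | Design effect | Effective n per arm | Power, normal | Power, 14 df |
|---|---|---|---|---|
| 0 | 7.10 | 174.6 | 0.908 | 0.864 |
| 0.01 | 8.03 | 154.4 | 0.871 | 0.820 |
| 0.02 | 8.96 | 138.4 | 0.834 | 0.777 |
| 0.05 | 11.75 | 105.5 | 0.725 | 0.662 |

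The 14-df reference alone lowers power from 0.908 to 0.864, before any organization correlation is allowed for.

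**Step 4. Type I error, by simulation.** There were 20,000 trials per cell, with REML on 40 site means and 2 or 3 sites per organization. The Monte Carlo standard error is about 0.2 points at 5–10%. The assumptions, none of them in the documents, are ρ of 0.02 or 0.05 and matched pairs sharing 0 to 75% of the organization variance. Months are collapsed to site means. Each cell gives the rate at ρ = 0.02 / 0.05.

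| Analysis | 0% shared | 30% | 50% | 75% |
|---|---|---|---|---|
| Site effect only, 38 df | 8.5% / 13.9% | 6.9% / 9.8% | 5.7% / 7.5% | 4.4% / 4.1% |
| Organization intercept, no pair, normal | 6.5% / 6.9% | 5.1% / 4.6% | 4.1% / 3.3% | 3.2% / 1.8% |
| Organization intercept, no pair, Satterthwaite (about 13–14 df) | 4.4% / 5.1% | 3.4% / 3.3% | 2.8% / 2.3% | 2.1% / 1.1% |

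The second row agrees with the exact value for a t statistic on 14 df judged against 1.96, which is 7.0%. A check with monthly binary data (30% reach, month-to-month autocorrelation 0.5) gave similar site-only rates: 8.3% / 13.0% at 0% shared and 5.8% / 7.3% at 50%.

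**The case against.** The strongest reply is that section 9 does provide for organization. It describes the Reach results as clustered by organization, and its case for a mixed model cites month-to-month correlation within a treatment organization. A reader might infer that the plan analyses sites and ignores the randomized unit. The documents do not support that: the site-only rates of 8.5% / 13.9% arise only if an analyst disregards the clustering phrase. They describe a misreading, not the evident intent. What is missing for Reach is the form of the term. For retention the levels themselves are missing.

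A reader might also infer that 0.90 power is out of reach. That is not shown either, because the loss depends on a correlation the documents do not give. For example, a single organization-level ICC of 0.03 with no extra site effect gives 0.93 on 14 df. Moreover, pairs are matched on prior technology uptake, rural sites and outpatient sites, and share a cohort, so zero benefit from matching is a pessimistic case.

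Finally, the simulations do not model retention or days of use, or any use of baseline data. These limits stand. They turn the size of the problem into a range, but they do not supply the missing specification.

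**Conclusion.** The point holds as a gap in specification that should be closed. Neither model gives a small-sample reference for 16 randomized organizations. The form of the organization term is open for Reach, and the levels are unnamed for retention. The stated power takes no account of correlation between sites of one organization or of the small number of randomized units.

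With organization modelled, no pair term and a normal reference, the excess false-positive risk is about 2 points at worst (7% against 5%). The test is nominal or conservative if matching explains a useful share of the organization variance. The larger site-only inflation belongs to the misreading, and it falls to about 5% or less if pairs share about 75% of that variance. Power on the randomized unit is about 0.86 to 0.66 for organization correlations from 0 to 0.05. The organization correlation, the benefit of matching and the split of sites within organizations are all assumptions.

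**What to change.** 1. In both the Reach and retention models, specify a random intercept for organization with sites nested within it. Keep it even if its variance is estimated as zero; at a correlation of 0.02 that happened in 21–23% of simulated trials. Test the arm effect with Satterthwaite or Kenward-Roger degrees of freedom (about 14). If a non-linear link is chosen, name an equivalent small-sample method, such as a t-test on organization-level summaries.
2. Restate the power on the randomized unit, with the assumed organization-level correlation written down and no credit for matching, for example from the 14-df column above.

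The plan should also say whether a pair term enters, decided before any comparison of outcomes by arm. Adding one is the sponsor's trade-off and not part of the required fix. It leaves 8 − 1 = 7 df. At correlations of 0.02 / 0.05, simulated power with pairs is 0.69 / 0.59, against 0.77 / 0.66 without, if pairs share nothing. If they share 75% it is 0.80 / 0.85 against 0.80 / 0.71. A pair term needs a reference on about 7 df, since a normal reference can give about 9% type I error.

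The cost is SAP wording only, because data are already collected by organization and site. The downsides are a lower stated power, which follows from randomizing 16 organizations, and a conservative test (down to about 1–2%) if matching is strong and pairs are not modelled.

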Patient-centered e-health has failed to achieve its promise despite considerable consumer interest in technology and research supporting its potential. E-health adoption rates in healthcare are poor, with specialty substance use disorder (SUD) treatment having the lowest technology adoption rate of any sector.¹ Implementation science can address this emerging gap in the e-health field by augmenting existing models, that explain organizational and individual ehealth behaviors retrospectively, with prospective models that can guide implementation. The organizational planning discipline, with its decades of research, could provide a cross-disciplinary “jump start” to developing an e-health implementation model for health organizations.^{2,3} Henry Mintzberg, a respected pioneer in this field, describes 2 beneficial approaches to planning: the *deliberate approach*, which is grounded in pre-implementation planning, and the *emergent approach* that is grounded in adapting to the environment as the plan is implemented.⁴ The proposed e-health implementation model, called the Network for the Improvement of Addiction Treatment–Technology Implementation (*NIATx-TI*) *Framework*, incorporates both approaches.

NIATx-TI was piloted in the Iowa Rural Health Information Technology Initiative (IRHIT) with 14 of Iowa’s 105 SUD treatment sites and resulted in a 2-fold increase in patients receiving distance treatment. The framework’s *deliberate* component includes using an organizational technology assessment⁵ and patient simulation.⁶ These tools identify and address assets and barriers to incorporate into the technology’s implementation protocol. The framework’s *emergent* component includes using a project team to uncover and prioritize implementation barriers as they arise, develop changes to address identified barriers, and monitor selected adoption measures, while receiving monthly coaching.

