2. STUDY OBJECTIVES

The specific aim of this study is to compare the effectiveness of NIATx-TI (Arm 2) and Product Training (Arm1) in implementing an evidence-based innovation (A-CHESS). Impact will be measured using the RE-AIM framework:⁵³

- Reach or Participation (Primary Outcome): a) percent and representativeness, based on age, gender, and ethnicity by organizational site, and b) A-CHESS use per each counselor, by days of use;
- Effectiveness: retention rates of eligible patients overall

- Adoption: percent and representativeness, based on age, gender, race, ethnicity, and education level of counselors referring and not referring patients to A-CHESS;
- Implementation: a) organizational readiness for, and b) fidelity of A-CHESS implementation; and c) qualitative and d) cost effectiveness analyses to develop a better understanding of the implementation processes for delivering NIATx-TI compared to product training alone; and
- Maintenance: A-CHESS use (e.g., A-CHESS downloads and days of A-CHESS use) during the post-test phase.

The specific aims of the COVID-19 supplemental study are 1) to understand whether using A-CHESS may help patients manage anxiety and loneliness associated with social isolation, physical distancing, and other changes to daily life during the COVID-19 pandemic, and 2) to understand how patients have adapted to changes in treatment modality during the COVID-19 pandemic. Impact will be measured by offering all patients who have ever signed up for an A-CHESS account the chance to complete an online survey (administered through REDCap) as well as the opportunity for a qualitative interview with a member of our research team using a standardized interview guide.

Study Coordination

The UW-Madison Center for Health Enhancement Systems Studies (CHESS) is the coordinating site for this study. The UW study coordinator will oversee all recruitment activities which includes:

- developing organizational site-specific recruitment and data collection processes that meet study objectives;
- training staff on protocol procedures prior to start of recruitment and continuous monitoring to assure compliance with the protocol and human subjects regulation;
- communicating with clinic site staff as needed via conference calls to monitor progress, inform of protocol changes/distribute new version of protocol, and address unanticipated issues or challenges;
- and manage all study data.

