3. SELECTION OF SUBJECTS

This study will engage SUD organizations, counseling and peer recovery support specialist staff at those organizations, and patients of those organizations.

Organizations: Sixteen SUD organizations in Iowa, with a total of forty sites, have agreed to participate in the project.

Counselors: The site coordinator will invite all outpatient counselors serving adult patients employed by the 16 SUD organizations to be part of the study as part of their role in the participating organizations. Any counselor may formally decline to participate during the training or any time thereafter.

Peer Recovery Support Specialists: Peer Recovery Support Specialists associated with the organization will be invited to be part of the study. Any Peer Recovery Support Specialists may formally decline to participate during training or any time thereafter.

Patients: We will aim to enroll 1,800 outpatients from the 16 enrolled organizations. Each organization is expected to have about 516 A-CHESS-eligible patients on average. We estimate that we will recruit a conservative 30% (or approximately 43 per organizational site) for a total n=1,800 patients in the study. We will recruit patients for the 18-month intervention period plus 6 months into the maintenance period. Patients are eligible for the study if they:

- Are 18+ years old
- Understand English
- Have a SUD diagnosis
- Have access to a smartphone

All patients will be offered the opportunity to complete a survey through REDCap. To date, n=520 patients have created an A-CHESS account. We will also conduct in-depth interviews with 40 patients who have created an A-CHESS account.

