5. TREATMENT PLAN

Treatment as Usual (TAU)/Control: Product Training/On-line Support – SUD organizational sites in the TAU or Control arm will participate in 1. day product implementation (or training) period sessions during Ms 11 - 15. On-line technical support will occur for the 18 months following product training.

Product training consists of two components: A-CHESS Demo and A-CHESS Product Training. During the A-CHESS Demo with the organization's IT, clinical leadership, and the A-CHESS site coordinator, the A-CHESS Product Trainer will:

- a) describe the features of A-CHESS (Tutorial)
- b) provide an A-CHESS organizational case example on how A-CHESS is implemented (including clinical protocols)
- c) provide examples of how to recruit and prepare clinicians and patients for A-CHESS

During the 1-hour A-CHESS Product Training, the organization's A-CHESS Site Coordinator and the A-CHESS Product Trainer will train the counselors and Peer Recovery Support Specialists at each site. Prior to the training, the site coordinator will present the Counselor and Peer Recovery Consent Form to each counselor as well as Peer Recovery Support Specialists and give them the opportunity to consent or decline to participate.

For those counselors that agree to participate, the training will include:

- a) demonstrating A-CHESS features and how A-CHESS allows patients to self-manage their recovery in conjunction with their counselor.
- b) role-playing (or patient simulation) live A-CHESS enrollment with counselors, where they can use the A-CHESS patient description sheet to guide conversations with patients
- c) demonstrating how to use the A-CHESS counselor dashboard.

Following the product training session, on-line technical support will be available. Patients and counselors can call or e-mail questions using the A-CHESS portal.

Counselor and Peer Recovery Support Specialist's role (same for Control and Intervention)

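### The .90 power takes the IRHIT gain as the NIATx-TI versus product-training difference, with no comparator or control-arm uptake stated; at the plan's own uptake figures it is nearer .80 or .72

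*Combined protocol and SAP*

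**What the plan says.** Section 2 sets the aim as to "compare the effectiveness of NIATx-TI (Arm 2) and Product Training (Arm1) in implementing an evidence-based innovation (A-CHESS"), with Reach as the primary outcome. Both arms receive product training, and Arm 2 adds NIATx-TI (section 8). The control arm is active. Section 5 gives it a demonstration, counselor training with role-played enrollment, and continuing help: "On-line technical support will occur for the 18 months following product training".

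Section 9 bases power on the "anticipated standardized effect size based on effects experienced in the IRHIT project". The one figure it uses is this: "The IRHIT pilot data found that NIATx-TI increased client technology use rates by 12.4% (increase of intervention success"), transformed to d = 0.352. With ICC 0.10, 20 sites per arm and 62 eligible patients per site, it concludes that "the study will achieve a power of .90 with a type I error rate of 0.05".

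The only other IRHIT result is in the opening summary, which says that the pilot, in 14 sites, "resulted in a 2-fold increase in patients receiving distance treatment". Neither place names a comparison group, and section 9 gives no control-arm rate.

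On expected uptake, section 3 says "We estimate that we will recruit a conservative 30" per cent. It also gives about 516 eligible patients per organization, 16 organizations and a target of 1,800 patients.

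**The concern.** The effect that matters is what NIATx-TI adds to product training. Section 9 takes a pilot gain with no stated comparator and uses it, undiminished, as that increment. Two things follow.

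- If the pilot gain was produced by a package that included product training, part of it will also appear in the control arm and drop out of the comparison.
- Whatever the comparator was, a fixed difference in percentage points is harder to detect at higher uptake (below 50%), because the binomial variance is larger. A power statement for a percentage needs a control rate, and there is none.

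At stake is how a null or small result on Reach is read. The protocol would present it as coming from a trial with 90% power for this contrast, which the documents do not establish.

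**Working it through.** **Inputs.** Section 9: 20 sites per arm, 62 patients per site, ICC 0.10, d = 0.352, type I error 0.05 (sidedness not stated; two-sided taken). Section 3: 516 eligible per organization, 16 organizations, target 1,800, and a stated 30%.

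**1. Reproduce the stated power.**
- Design effect = 1 + (62 − 1) × 0.10 = 7.1.
- Effective patients per arm = 20 × 62 / 7.1 = 174.6.
- Power = Φ(0.352 × √(174.6/2) − 1.96) = Φ(3.289 − 1.96) = 0.908. A t reference with 38 df gives 0.893.

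So .90 reproduces, with the whole of 0.352 taken as the difference between arms. One-sided testing would give 0.950, so the two-sided reading fits. The smallest d with .90 power is (1.960 + 1.282)/√(174.6/2) = 0.347, which leaves almost no reserve.

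**2. Uptake implied by section 3.**
- 516 × 16 = 8,256 eligible; 1,800 / 8,256 = 21.8%.
- The text itself states 30%.

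These two rates do not agree, so both are carried forward.

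**3. Grant the full 12.4 points as the difference between arms.** Let p̄ be overall uptake, with arms at p̄ ± 6.2 points and n = 174.6 per arm:
- SE₀ = √(2p̄(1 − p̄)/n)
- SE₁ = √((p₁(1 − p₁) + p₂(1 − p₂))/n)
- Power = Φ((0.124 − 1.96 × SE₀)/SE₁)

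| Overall uptake | Control vs NIATx-TI | 0.124/√(p̄(1 − p̄)) | SE₀ | SE₁ | Power |
|---|---|---|---|---|---|
| 14.5% | 8.3% vs 20.7% | 0.352 | 0.0377 | 0.0371 | 0.91 |
| 21.8% | 15.6% vs 28.0% | 0.300 | 0.0442 | 0.0437 | 0.80 |
| 30% | 23.8% vs 36.2% | 0.271 | 0.0490 | 0.0486 | 0.72 |

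Using SE₁ throughout instead, Φ(0.124/SE₁ − 1.96), gives 0.92, 0.81 and 0.72. The first row is where 12.4 points correspond to d = 0.352. By this formula power drops below .90 once overall uptake passes about 15%.

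**4. Smaller differences, as assumptions.** The same formula at 21.8% and 30% overall uptake gives 0.62 and 0.53 for a 10-point difference, and 0.44 and 0.37 for 8 points.

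**5. If part of the 12.4 points belongs to product training.** The documents give no share and do not show how 12.4% became 0.352. Suppose the share were half, leaving 6.2 points:
- scaling d in proportion gives 0.352 × 6.2/12.4 = 0.176 and power 0.38;
- 0.352 also equals √0.124, and that conversion applied to 6.2 points gives √0.062 = 0.249 and power 0.64.

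The direction is clear; the size is not.

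**The case against.** The strongest reply is that the IRHIT design is not described, so nothing shows that 12.4% is a before-after gain. The 2-fold increase concerns distance treatment, and the documents do not say it is the same measure as the technology use rates in section 9. The 12.4% could already be a net difference between groups. Product training is given in both arms, so uptake common to both cancels. It reduces the difference only if the pilot figure contains a product-training share. Section 5 does say the framework includes product training, but it is describing this trial's intervention arm; the opening summary and section 8 treat the two as separate. All of this stands.

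It rules out several stronger readings that a reader might infer:
- That .90 is the power against a control that does nothing. The documents do not show this.
- That the plan assumes no control uptake. It never says so. With controls at zero, Arm 2 would need 1,800/4,128 = 43.6% to reach the target, which shows only that control uptake is expected. Overall uptake of 21.8% or 30% is compatible with a full 12.4-point difference.
- That power is .86, .79 or .70 if product training accounts for 1, 2 or 3 points. Those values come from scaling d in proportion; the square-root conversion gives .88, .85 and .82. Both rest on an assumed share.

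Two further replies concern the calculation. First, section 9 plans a mixed model on monthly data and also analyses frequency of use, which is not a proportion. That is so, but section 9 claims no gain from repeated measures, and its .90 comes out of the simple clustered calculation. Second, section 3 implies 516 × 16/40 = 206.4 eligible patients per site, not 62. With 206.4, effective n is 20 × 206.4/(1 + 205.4 × 0.10) = 191.6 per arm, and step 3 gives about 0.84 and 0.76. Still short of .90.

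**Conclusion.** The concern holds in a limited form. The arithmetic behind .90 is right for d = 0.352; what is unsupported is stating it without conditions as the power for NIATx-TI over product training. On the reading most favourable to the plan, with the full 12.4 points as the difference between arms, power is about .80 to .81 at 21.8% overall uptake and .72 at 30%. It is .90 or more only at about 15% or below.

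This rests on reading 12.4% as percentage points, two-sided 0.05, the section 9 cluster inputs, and the percentage of eligible patients as the outcome being powered. A further loss follows if the pilot gain includes product training, but neither that condition nor its size can be settled from the documents.

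**What to change.** In section 9:

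1. State what the IRHIT 12.4% was measured against, whether it is in percentage points, and how it was converted to 0.352. If the pilot had a product-training comparison, size on that difference.
2. State an assumed control-arm uptake consistent with section 3, after settling whether section 3 means 21.8% or 30%.
3. Replace the unconditional claim of .90 with the power for NIATx-TI over product training at that control rate, across a range of between-arm differences labelled as assumptions. The calculations in steps 3 and 4 of the working can serve as a template.
4. Do not write in .86, .79 and .70 as fixed results; no documented figure supports the product-training shares behind them.

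The cost is a short recalculation and a protocol wording change, with no added sites or patients. The drawback is that the stated power becomes less favourable.
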